**Description and Derivation of Other Secondary Outcomes**

Measure	Variable	Derivation / Comment	Definition of Missing
	Number of days with supplemental oxygen use	Total number of days patients' NIAID-OS is $\geq 5$	Missing if any observed NIAID-OS is missing.
	Proportion of patients in each severity category	Total proportion of patients in each NIAID-OS category at particular time points	Missing if observed NIAID-OS is missing at particular time point.
	Patients with at least 2-point improvement on the NIAID-OS or live discharge from the hospital	Proportion of patients whose baseline NIAID-OS - observed NIAID-OS $\geq 2$	Missing if observed NIAID-OS is missing or if observed NIAID-OS is $\geq 3$ and baseline NIAID-OS is missing
	Patients with at least 1-point improvement on the NIAID-OS or live discharge from the hospital	Proportion of patients whose observed NIAID-OS is $\leq 2$ or whose baseline NIAID-OS - observed NIAID-OS $\geq 1$	Missing if observed NIAID-OS is missing or if observed NIAID-OS is $\geq 3$ and baseline NIAID-OS is missing
Intensive Care Unit (ICU) stay	Duration of stay in the intensive care unit (ICU)	Total number of days spent in the ICU plus days from death up to and including Day 28.	Missing if status of ICU stay is missing for any day for the patients and the patient is alive.
Fever	Time to resolution of fever	
Time to patients being free of fever for the first time for patients who had fever at baseline.
 
Fever resolution is defined by:
 
 
• <math>\leq 36.6^{\circ}\text{C}</math> (axilla, forehead)
 
• <math>\leq 37.2^{\circ}\text{C}</math> (oral cavity), or
 
• <math>\leq 37.8^{\circ}\text{C}</math> (rectum, ear, temporal artery)
 
 
If temperature is assessed multiple times in a day, fever will be considered to be resolved if all of the measurements fall in the “fever resolution” ranges defined above
	Missing if fever status is missing or baseline fever status is missing and time to event of interest cannot be identified using remaining data.
National Early Warning Score (NEWS)	Mean change	
Mean of observed NEWS – NEWS at baseline
 
NEWS will be calculated using aggregate score approach in Royal College of Physicians [WWW].
	Missing if either baseline or observed NEWS component is missing.

## Description and Derivation of Other Secondary Outcomes

Measure	Variable	Derivation / Comment	Definition of Missing
Extubation	Time to definitive extubation	
Patients included: randomized patients who progress to OS 7 at any time on or prior to Day 27.
 
Start date: first date that patient progressed to OS 7 (this could be their baseline date if they progressed the first day on study, after baseline)
 
Event date: First date when patient is removed from invasive mechanical ventilation (i.e., OS 6 or less) for the last time on or prior to Day 28.
 
Censor date for patients who are OS 7 at their last observation or by Day 28: Date of last observation.
 
Censor date for patients who die after their Start Date: Date of what would have been their Day 28.
	Missing if NIAID-OS is missing and time to event of interest cannot be identified using remaining data.
Oxygen Saturation	Time to oxygen saturation $\geq 94\%$ on room air in days	
Patients included: randomized patients whose oxygen saturation (based on NEWS) is <math>< 94\%</math> at baseline.
 
Event Date: the first date that their oxygen saturation is <math>\geq 94\%</math> and their OS is <math>\leq 4</math>.
	Missing if NIAID-OS is missing or oxygen saturation status is missing and time to event of interest cannot be identified using remaining data.
Resting respiratory rate	Number of days of resting respiratory rate $< 24$ breaths per minute	
Total number of days when patients' resting respiratory rate <math>< 24</math> breaths per minute.
 
This will be based on values from NEWS.
	Missing if Patient's resting respiratory rate is missing for at least 1 day.

Abbreviations: ICU = intensive care unit; NIAID-OS = National Institute of Allergy and Infectious Diseases ordinal scale.

Table KHAA.6.7. Description of Other Secondary Analyses

Measure	Variable	Population	Analysis Method	Time Point	Analysis Type
NIAID-OS	Time to recovery by disease duration at baseline: < 7 days and ≥7 days	ITT	Log rank test using IETI	By Day 28	Secondary analysis
			Cox Proportional Hazards model using IETI	By Day 28	Supportive analysis
	Time to clinical deterioration	ITT	Log rank test	By Day 28	Secondary analysis
			Cox Proportional Hazards model	By Day 28	Supportive analysis
	Time to clinical improvement in one category	ITT	Log rank test using IETI	By Day 28	Secondary analysis
			Cox Proportional Hazards model using IETI	By Day 28	Supportive analysis
	Overall improvement	ITT	Proportional Odds model using MI	Day 21 and Day 28	Secondary analysis
			Proportional Odds model using LOCF	Day 21 and Day 28	Supportive analysis
	Time to independence from noninvasive mechanical ventilation	ITT	Log rank test using IETI	By Day 28	Secondary analysis
			Cox Proportional Hazards model using IETI	By Day 28	Supportive analysis
	Time to independence from oxygen therapy in days	ITT	Log rank test using IETI	By Day 28	Secondary analysis
			Cox Proportional Hazards model using IETI	By Day 28	Supportive analysis
	Number of days with supplemental oxygen use	ITT	ANOVA with MI	By Day 28	Secondary analysis
			Wilcoxon Rank Sum Test using LOCF	By Day 28	Supportive analysis
	Proportion of patients in each severity category	ITT	Observed	Day 4,7,10,14	Secondary analysis
			Descriptive using LOCF	Day 4,7,10,14	Supportive analysis
	Patients with at least 2-point improvement on the NIAID-OS or live discharge from the hospital	ITT	Logistic regression using MI	Day 4, 7, 10, 14, 21, 28	Secondary analysis
			Logistic regression using LOCF	Day 4,7,10,14, 28	Supportive analysis
	Patients with at least 1-point improvement on the NIAID-OS or live discharge from the hospital	ITT	Logistic regression using MI	Day 28	Secondary analysis
			Logistic regression using LOCF	Day 28	Supportive analysis

Measure	Variable	Population	Analysis Method	Time Point	Analysis Type
Intensive Care Unit (ICU) stay	Duration of stay in the intensive care unit (ICU)	ITT	Wilcoxon Rank Sum Test using LOCF	By Day 28	Secondary analysis
Fever	Time to resolution of fever	ITT	Log rank test using IETI	By Day 28	Secondary analysis
			Cox Proportional Hazards model using IETI	By Day 28	Supportive analysis
National Early Warning Score (NEWS)	Mean change from baseline in NEWS	ITT	MMRM	Day 4,7,10,14	Secondary analysis
base	Time to definitive extubation	ITT	Log rank test using IETI	By Day 28	Secondary analysis
			Cox Proportional Hazards model using IETI	By Day 28	Supportive analysis
Oxygen Saturation	Time to oxygen saturation $\geq 94\%$ on room air in days	ITT	Log rank test using IETI	By Day 28	Secondary analysis
			Cox Proportional Hazards model using IETI	By Day 28	Supportive analysis
Resting respiratory rate	Number of days of resting respiratory rate $< 24$ breaths per minute	ITT	Wilcoxon Rank Sum Test using observed data.	By Day 28	Secondary analysis

Abbreviations: ANOVA = analysis of variance; IETI = infinite event time imputation; ITT = Intent-to-Treat; MI = multiple imputation; LOCF = last observation carried forward; MMRM = mixed-effect model repeated measure; NIAID-OS = National Institute of Allergy and Infectious Diseases ordinal scale.

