### Other medical conditions or history

- [13] Require invasive mechanical ventilation, including ECMO at study entry.
- [14] Current diagnosis of active malignancy that, in the opinion of the investigator, could constitute a risk when taking investigational product.
- [15] Have a history of VTE (deep vein thrombosis [DVT] and/or pulmonary embolism [PE]) within 12 weeks prior to randomization or have a history of recurrent (>1) VTE (DVT/PE).
- [16] Anticipated discharge from the hospital, or transfer to another hospital (or another unit), which is not a study site within 72 hours after study entry.

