### **6.4.1. Infinite Event Time Imputation (IETI)**

For some time-to-event endpoints, if there are competing risks to the event of interest, then the event times censored due to the competing risk will be imputed as infinite.

This imputation method will be applied if the event of interest is in the opposite direction of death (e.g., recovery or improvement). For time to recovery or time to improvement, all deaths

within 28 days will be considered censored at Day 28 with respect to time to event of interest. Conceptually, a death corresponds to an infinite time to event of interest, but censoring at any time greater than or equal to Day 28 gives the same answer as censoring at Day 28; both correspond to giving death the worst rank.

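### Time to definitive extubation is tested between arms in a subset formed after randomisation but labelled ITT, so the result can point against a drug that prevents intubation

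*SAP*

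**What the plan says.** SAP Table KHAA.6.6 defines the analysis set for time to definitive extubation as "Patients included: randomized patients who progress to OS 7 at any time on or prior to Day 27". The clock is specific to each patient: "Start date: first date that patient progressed to OS 7". The event is the last removal from invasive ventilation by Day 28. Survivors still ventilated leave at their last observation. For deaths the rule is "Censor date for patients who die after their Start Date: Date of what would have been their Day 28".

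Protocol Section 5.2, criterion 13, excludes patients who "Require invasive mechanical ventilation, including ECMO at study entry". The Addendum 5 patients, who are at OS 7 at baseline, did not progress to that state and have their own analyses in SAP Appendix 3. Reaching OS 7 after randomisation counts as an event in the primary endpoint (SAP Table KHAA.6.4).

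Table KHAA.6.7 gives the population as ITT and plans a log-rank test as the secondary analysis and a Cox model as supportive, both using infinite event time imputation (IETI). SAP Section 6.2.3 makes the log-rank test unstratified and adjusts the Cox model for the baseline stratification variables. The default level is two-sided 0.05 (Section 6.1). The endpoint is outside the family controlled for multiplicity (Section 6.6).

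Section 6.4.1 justifies IETI by saying that "censoring at any time greater than or equal to Day 28 gives the same answer as censoring at Day 28" and that "both correspond to giving death the worst rank".

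**The concern.** Randomisation balances the arms at Day 1. It does not balance those patients in each arm who later need a ventilator, because the drug is meant to change who they are. If baricitinib keeps some milder patients off the ventilator, the intubated baricitinib patients are sicker on average than the intubated placebo patients, and they come off more slowly even if the drug does nothing after intubation. A log-rank test and hazard ratio in this subset then measure case mix as well as treatment. By symmetry, a drug that pushed extra milder patients onto a ventilator would appear to speed extubation.

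Nothing in the SAP limits the interpretation of this endpoint, and the ITT label invites the reader to treat the p-value as a randomised comparison. A nominal harm or benefit on weaning could be reported that is only selection. The neighbouring endpoints on independence from non-invasive ventilation and from oxygen avoid this: their subsets are defined by baseline OS, and their clock starts at baseline.

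**Working it through.** **Inputs from the documents.** About 1400 patients randomised 1:1, so about 700 per arm; nobody on invasive ventilation at entry; analysis set, clock and tests as above. The documents state no sample size, event count or power for this endpoint, so there is no planned figure to reproduce.

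**Assumed inputs (none is in the documents).** On placebo, 52 mild and 52 severe intubations: 104/700 = 14.9% of the arm. Daily chance of extubation and of death: 10% and 1% if mild, 3% and 6% if severe. Intubation between Day 2 and Day 14. The drug prevents 0%, 40% or 60% of the mild intubations, harms nobody, and has no effect after intubation.

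**Step 1: case mix by arm.** The mild share of intubated patients is 52/104 = 50% on placebo. With 40% of mild intubations prevented it is 31.2/83.2 = 37.5% on baricitinib; with 60% prevented, 20.8/72.8 = 28.6%.

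**Step 2: extubation by 14 days.** With constant daily hazards e (extubation) and d (death), cumulative incidence is e/(e+d) × [1 − (1−e−d)^14].
- Mild: (0.10/0.11)(1 − 0.89^14) = 73.1%.
- Severe: (0.03/0.09)(1 − 0.91^14) = 24.4%.
- Placebo: 0.500 × 73.1 + 0.500 × 24.4 = 48.8%.
- Baricitinib, 40% prevented: 0.375 × 73.1 + 0.625 × 24.4 = 42.7%.
- Baricitinib, 60% prevented: 0.286 × 73.1 + 0.714 × 24.4 = 38.3%.

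Simulation under the SAP rule gives 49%, 42% and 39%. The apparent disadvantage of 6 to 10 points comes entirely from patients who were spared a ventilator.

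**Step 3: the planned log-rank test.** Simulated under the SAP's event and censoring rules:

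| Mild intubations prevented | Mean log-rank Z | Nominally significant for placebo |
|---|---|---|
| 0% | −0.01 | about 1% |
| 40% | −0.94 | 11.6% (about 13% in an independent repeat) |
| 60% | −1.42 | 25.9% (about 29% in the repeat) |

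The 1% is below the nominal 2.5% in one direction because this simulation fixes the numbers of mild and severe patients per arm. In Step 4, where they vary, the no-effect rate is 2.1 to 2.6%.

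**Step 4: a second set of assumptions.** 10 to 20% of placebo patients intubated, half mild (25% die, mean 7 days to extubation) and half severe (65% die, mean 14 days).

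| Mild intubations prevented | Extubation hazard ratio | Estimate favours placebo |
|---|---|---|
| 0% | 1.00 | about half of trials |
| 30% | 0.88–0.90 | 71–74% |
| 50% | 0.79–0.80 | 80–87% |
| 70% | 0.68–0.70 | 91–97% |

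With 50% prevented and 15% intubated on placebo, baricitinib has about 79 intubations against 106 and 38 deaths among them against 45, yet the extubation hazard ratio is about 0.80 against it. In the 50% scenario, ventilator-free days in all randomised patients favour baricitinib by 0.27, 0.43 and 0.54 days at placebo intubation rates of 10%, 15% and 20%.

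**Step 5: the Section 6.4.1 justification.** By the interval formula in SAP Section 6.1.3, a death in a patient intubated on Day 20 is censored at 28 − 20 + 1 = 9 days on this clock, while a patient intubated on Day 2 can be followed for 28 − 2 + 1 = 27 days. The death is therefore not ranked behind every extubation. In simulated data with a baseline clock, Z = 0.7077 whether deaths are censored at 28, 60 or 1000. With an intubation clock, Z = −0.4621 under the SAP rule and −0.4326 with later censoring. The stated equivalence does not literally hold for this endpoint.

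**The case against.** The strongest defence has four parts.

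- **The subset is disclosed and the endpoint is minor.** Table KHAA.6.6 states the restriction, and Table KHAA.6.7 writes ITT on every row, including others restricted to a subset. The endpoint carries no controlled alpha and cannot affect trial success. This lowers the severity. However, the other restricted rows that use ITT loosely (such as baseline OS 6 or baseline fever) are defined at baseline and remain randomised comparisons.
- **The right comparison is already planned.** Ventilator-free days and all-cause mortality are ITT key secondaries, and progression to ventilation is in the primary. That stands, and it makes the fix cheap. It does not make the extubation test valid.
- **The Cox model is adjusted.** Baseline severity, age, region and steroid use may lessen the imbalance; an adjusted Cox model was not simulated. They cannot remove selection through severity they do not capture, and the log-rank test, which is the main analysis here, is unadjusted.
- **The magnitudes rest on assumed inputs.** True. The direction follows whenever prevention is concentrated in milder patients; the size does not.

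A reader might also infer from the gap in Section 6.4.1 that censoring deaths at Day 28 inflates the estimated extubation probability. The documents do not support that. Ventilated survivors also leave no later than Day 28, so holding deaths to the same administrative end estimates the cumulative incidence with death competing. For severe patients intubated on Days 15 to 22, the true 13-day value is (1/3)(1 − 0.91^13) = 23.55%. The SAP rule gives 23.52%. Keeping deaths in the risk set to the longest follow-up gives 20.85%, which is too low, so that is not a remedy.

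**Conclusion.** The point holds on selection. Time to definitive extubation is compared in patients chosen by a post-randomisation event that the drug is intended to prevent, so its log-rank p-value and hazard ratio are not a randomised comparison despite the ITT label. If prevention is concentrated in milder patients, the test can point against a beneficial drug: nominally significant for placebo in roughly 12 to 29% of trials with 40 to 60% of mild intubations prevented, against about 1% with no drug effect. These figures rest on the assumed intubation counts, case mix and daily hazards. With no intubations prevented there is no bias.

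On the death rule, the conclusion is only that the same-answer and worst-rank reasoning of Section 6.4.1 does not literally hold when the clock starts at intubation. The consequence of the whole point is limited to one ungated secondary endpoint; the primary conclusion is not threatened.

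**What to change.** In SAP Tables KHAA.6.6 and KHAA.6.7:

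- Remove the log-rank p-value and the Cox hazard ratio for time to definitive extubation.
- Report extubation descriptively by arm, as cumulative incidence with death as a competing outcome.
- Replace the ITT label on this row with: post-randomisation subset, not a randomised comparison.
- State that the between-arm question is answered by the ventilator-free-days analysis already planned in all randomised patients.

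This is a wording change that needs no new data. The protocol endpoint stays, and Protocol Section 9.4 allows a change of method that is not a principal feature to be described and justified in the SAP and study report. The cost is that one ungated other secondary endpoint loses its p-value.

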Physical examination	X										The complete physical exam is performed if feasible (excludes pelvic, rectal, and breast exams). An assessment of risk factors for tuberculosis (TB) is included (Section 8.2.2).
Symptom-directed physical examination		Х	Х	Х	Х	Х			Х		See Section 8.2.2.
Chest imaging (CT scan or x-ray) (local)	X			Х					Х	Х	Assessed by radiologist or pulmonologist (Section 8.2.4). Documentation of hospital-based imaging prior to study entry, obtained up to 24 hours prior to study entry is acceptable.

Study day	1	4	7	10	14	28	Follow-up (28 Days after Last Dose)	Follow-up Day 60	ETV	Unsched uled	Comments
Interval tolerance (days)	≤3	_	_	_		_	±4	+7	_	_	If patient is discharged from hospital, the study visit may include a visit interval tolerance (window) of $\pm 2$ at Study Day 4, Day 7, Day 10, Day 14, and Day 28.
Site Visit		X	X	X	X	X					Site visit is preferred after discharge, but telephone visit is acceptable after discharge and should include collection of concomitant medications, adverse events, COVID-19 clinical symptoms, and Clinical Status Assessment. Failure to conduct activities that cannot be reasonably performed over the telephone will not be considered a protocol deviation.
Telephone Visit							Х	Х			
12-lead ECG (local)	Х										Performed and assessed locally. Documentation of hospital-based ECG prior to study entry, up to 24 hours prior to study entry is acceptable (Section 8.2.3).
Clinician-Administered Assessments Paper											
Clinical Status Assessment	Х	Х	Х	X	Х	Х		Х	Х		Document daily through Day 29. Includes status of oxygen/life support procedures and proning.
Assessment for the NEWS	Х	Х	Х	Х	Х	Х			Х		Document daily.
Laboratory Tests and Sample Collections											For laboratory tests and sample collections, the timing can be +1 day or -1 day from the designated day, unless otherwise specified.
Hematology	Х	х	х	x	х	x			Х	Х	Performed locally. Tests performed in the 24 hours prior to study entry will be accepted for determination of eligibility. Unscheduled collection, if clinically warranted, will be entered into the eCRF.

Study day	1	4	7	10	14	28	Follow-up (28 Days after Last Dose)	Follow-up Day 60	ETV	Unsched uled	Comments
Interval tolerance (days)	≤3	_	_	_	_	_	±4	+7	_	_	If patient is discharged from hospital, the study visit may include a visit interval tolerance (window) of $\pm 2$ at Study Day 4, Day 7, Day 10, Day 14, and Day 28.

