Laboratory Tests and Sample Collections (continued)											For laboratory tests and sample collections, the timing can be +1 day or -1 day from the designated day, unless otherwise specified.
Procalcitonin	Х	Х	х	Х	х	Х			Х	Х	Performed locally. Test performed in the 24 hours prior to study entry will be accepted for determination of eligibility. Unscheduled collection, if clinically warranted, will be entered into the eCRF.
SARS-CoV-2 viral infection confirmation via NP swab	Х	Х		Х	Х	Х			Х	Х	Performed locally. Test performed during current hospitalization (prior to study entry) will be accepted for determination of eligibility per inclusion criteria requirements. Collection of NP swab is at investigator's discretion at other timepoints and will not be considered protocol deviation if not done.
Exploratory biomarker samples: serum, whole blood	Х	Х	Х	Х					Х		Obtained and sent to the Lilly- designated laboratory. Refer to Section 8.8 for additional information.
Exploratory biomarker sample: nasopharyngeal swab	Х	Х		Х	Х	Х			Х		Obtained and sent to the Lilly- designated laboratory. Refer to Section 8.8 for additional information.

Study day	1	4	7	10	14	28	Follow-up (28 Days after Last Dose)	Follow-up Day 60	ETV	Unsched uled	Comments
Interval tolerance (days)	≤3		—	_		_	±4	+7	—	_	If patient is discharged from hospital, the study visit may include a visit interval tolerance (window) of $\pm 2$ at Study Day 4, Day 7, Day 10, Day 14, and Day 28.
Site Visit		X	X	x	x	X					Site visit is preferred after discharge, but telephone visit is acceptable after discharge and should include collection of concomitant medications, adverse events, COVID-19 clinical symptoms, and Clinical Status Assessment. Failure to conduct activities that cannot be reasonably performed over the telephone will not be considered a protocol deviation.
Telephone Visit							Х	Х			
Randomization	Х										Dosing daily from randomization through Day 14, or until patient is discharged from hospital, whichever comes first.

Abbreviations: CT = computerized tomography; eCRF = electronic case report form; ECG = electrocardiogram; eGFR = estimated glomerular filtration rate; ETV = early termination (discontinuation) visit; ICU = intensive care unit; ICF = informed consent form; MDRD = Modification of Diet in Renal Disease; NEWS = National Early Warning Score; NP = nasopharyngeal; NSAIDs = nonsteroidal anti-inflammatory drugs; VTE = venous thromboembolism; WOCBP = women of childbearing potential.

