## 8.2.1. Vital Signs

Vitals signs (body temperature, blood pressure, heart [pulse] rate, respiration rate, oxygen saturation) will be assessed and documented daily, and as clinical indicated, and entered into the eCRF as specified in the SoA (Section 1.3) and as clinically indicated.

These include the minimum/maximum vital signs daily (including temperature, respiratory rate, oxygen saturation).

The most recent measurements prior to study drug administration will be used to calculate the NEWS. Vital signs should be performed at approximately the same time each day.

Additional vital signs may be measured during the study visits if warranted, as determined by the investigator and/or appropriate designee.

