### 6.1.2. Definition of Study Baseline

Unless otherwise specified, for efficacy and health outcomes, baseline is defined as the last nonmissing assessment recorded on or prior to, the first date that clinical status is assessed.

Baseline for safety analyses is described in [Table KHAA.6.8](#).

Change from baseline will be calculated as the visit value of interest minus the baseline value. If a baseline value or the value at the visit is missing for a variable, then the change from baseline is defined as missing.

The baseline of vital signs is defined as the vital signs collated at Day 1 from the case report form (CRF) Assessment for the National Early Warning Score (NEWS) (AVPU1001\_VS1001\_F1). The post baseline vital signs for analyses other than NEWS is defined as vital signs collated from CRF Vital Signs: Minimum and Maximum (VS1001).

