## **6.4. Handling of Dropouts or Missing Data**

The following imputation rules will be used for subjects who are lost to follow-up, withdrew from the study early, or do not have further outcome data available after discharge for any reason or death.

Efforts to use all available data and minimize missing data imputation will be considered. For clinical outcomes related to National Institute of Allergy and Infectious Diseases ordinal scale (NIAID-OS), the outcome may be derived using pre-specified relevant clinical data before missing data imputation approaches applied.

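### Days with respiratory rate below 24: absent readmission, the any-day-missing rule drops every patient discharged by Day 26 or dead before Day 28 from an analysis labelled ITT

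*SAP*

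**What the plan says.** The endpoint is the number of days, over Day 1 to Day 28, on which the resting respiratory rate is below 24 per minute (SAP 4.2, other secondary).

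- **Derivation (SAP Table KHAA.6.6):** the source is given as "This will be based on values from NEWS" and the missing-data definition is "Missing if Patient's resting respiratory rate is missing for at least 1 day".
- **Analysis (SAP Table KHAA.6.7):** population ITT, by Day 28, "Wilcoxon Rank Sum Test using observed data". The row assigns no multiple imputation, LOCF or death rule.
- **ITT (SAP 6.1.1):** all participants randomly assigned, analysed as assigned.
- **General missing-data text (SAP 6.4):** its imputation rules are introduced as covering, among others, subjects who "do not have further outcome data available after discharge for any reason or death".
- **Data collection (Protocol 1.3):** vital signs, including respiratory rate, are assessed daily while the patient is hospitalised. After discharge the visits up to Day 28 are those at Days 4, 7, 10, 14 and 28, each with a window of ±2 days. They may be by telephone, and the listed telephone content contains no vital signs. The NEWS row says "Document daily".

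**The concern.** Under the rule as written, one missing day makes the whole count missing, and a test on observed data then omits the patient. Most days after discharge, and all days after death, have no respiratory rate. Who is analysed is therefore decided after randomisation by discharge and survival, both of which the drug may change. The row would be reported as ITT while describing mainly patients still in hospital at about Day 27 or 28.

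The other day-count rows avoid this. Ventilator-free days, duration of hospitalisation and days with supplemental oxygen also use an any-day-missing definition, but they are assigned multiple imputation with an LOCF supportive analysis. ICU stay is assigned LOCF and counts the days from death to Day 28. The respiratory-rate row is the only day count with no imputation method.

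**Working it through.** The plan gives no figure for this endpoint, so there is none to reproduce. The check asks which patients can have all 28 days recorded.

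**Inputs.** Window Day 1 to Day 28 (SAP 4.2). Daily rates in hospital, taken as complete. Post-discharge visits at Days 4, 7, 10, 14 and 28, ±2 days (Protocol 1.3). No readmission.

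**Formula.** For discharge on day d, minimum missing days = (28 − d) − (the most post-discharge days that on-site visits can cover, one day per visit, using the windows). This is the best case; if every visit is by telephone, missing days = 28 − d. For death on day d, minimum missing days = 28 − d.

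| Discharge day | Days left | Most coverable on site | Minimum missing |
|---|---|---|---|
| 1 | 27 | 5 | 22 |
| 7 | 21 | 4 | 17 |
| 14 | 14 | 2 | 12 |
| 25 | 3 | 1 | 2 |
| 26 | 2 | 1 | 1 |
| 27 | 1 | 1 | 0 |

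Death on Day 14 leaves 14 missing days, on Day 27 leaves 1, and on Day 28 can leave 0. The boundaries are therefore exact: discharge on or before Day 26, or death before Day 28, always gives a missing value. Discharge on Day 27 escapes only if the Day 28 visit is on site on Day 28.

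**Number excluded.** The documents give no discharge or death distribution. For assumed excluded shares: 1400 × (1 − 0.50) = 700 remain; 1400 × (1 − 0.75) = 350; 1400 × (1 − 0.95) = 70.

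**What if analysts summed the recorded days instead?** Table KHAA.6.6 does not say this, but it is an obvious workaround. With visits on nominal days and every rate below 24:

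- Discharge on Day 5: 5 + 4 later visits (Days 7, 10, 14, 28) = 9 days, or 5 by telephone.
- Discharge on Day 10: 10 + 2 later visits (Days 14, 28) = 12 days, or 10 by telephone.

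The earlier discharge scores 3 to 5 good days fewer. How this affects the test depends on assumptions. The illustration below uses 700 patients per arm, no deaths, a lognormal discharge day capped at Day 28, medians 9 versus 10 days, and a two-sided Wilcoxon test at 0.05:

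| Assumed setting | Significant against the faster arm |
|---|---|
| Log-SD 0.6, every rate below 24 | about 88–89% |
| Log-SD 1.0, up to half of hospital days at 24 or above | about 44–51% |
| Log-SD 0.6, first 75% of hospital days at 24 or above, site visits | about 12.5% |
| First 90% of hospital days at 24 or above, site visits | 0%; about 39% (log-SD 1.0) to 70% (log-SD 0.6) favour the faster arm |

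With telephone visits and log-SD 0.6, the figure against the faster arm stays above 80% even when 75% or 90% of hospital days are at 24 or above. With equal medians of 10 days, log-SD 0.6 and every rate below 24, rejection is 4.8–5.8%. Summing therefore keeps type I error when discharge is unaffected, but its size and sign under a real effect are not fixed.

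**The case against.** **The table entry may be a deliberate choice.** A reader might infer that the row flatly contradicts SAP 6.4. The text does not support that. The sentence quoted from 6.4 is a general opening, and the rules under it limit themselves: 6.4.1 to some time-to-event endpoints, 6.4.2 to some analyses, 6.4.3 to NIAID-OS scores. The same section also aims to minimise imputation. What remains is tension with a general statement. But a deliberate complete-case analysis is still not ITT as 6.1.1 defines it.

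**NEWS is documented daily.** The NEWS row lacks the in-hospital limit of the vital-signs row, so the absence of daily rates at home is an inference. It is a sound one: Protocol 8.1.3.1 derives NEWS from data already entered in the eCRF, vital signs are daily only in hospital, and telephone contacts do not collect them. A reader might go further and argue that NEWS ends with dosing, because Protocol 8.2.1 says "The most recent measurements prior to study drug administration will be used to calculate the NEWS" and the schedule says "Dosing daily from randomization through Day 14, or until patient is discharged from hospital, whichever comes first". That fails, because NEWS is scheduled on Day 28, after dosing has ended.

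**Source form.** SAP 6.1.2 says "The post baseline vital signs for analyses other than NEWS is defined as vital signs collated from CRF Vital Signs: Minimum and Maximum", and a reader might infer an unresolved conflict of sources. The endpoint's own row names NEWS, and the specific entry governs.

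**Validity under no effect.** If treatment affects neither discharge nor death, exclusion falls alike on both arms and the literal analysis is valid. This stands.

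**Importance.** The endpoint is outside the testing scheme in SAP 6.6. This also stands and limits the weight of the point.

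**Conclusion.** The point holds. Taken together, the two table entries exclude, absent readmission, every patient discharged on or before Day 26 or dead before Day 28, and the result is not an ITT comparison. The cut-offs follow from the visit schedule even if every remaining visit is on site. They rest on respiratory rate not being obtained at home between visits.

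The harm is selection. If treatment changes discharge or survival, the arms in the analysed set are no longer comparable, and the documents do not determine the direction of bias. The number excluded is unknown; 700 to 70 remaining of 1400 reflects assumed shares only.

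A reader might infer that the planned analysis would very probably count against a drug that speeds discharge, at 88–89%. The documents do not support this. That figure belongs to summing recorded days, which Table KHAA.6.6 rules out, and under other plausible inputs it falls to 0% or reverses.

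Primary and key secondary conclusions are unaffected. The wording should be corrected so that this one reported result does not mislead.

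**What to change.** In Tables KHAA.6.6 and KHAA.6.7, replace the any-day-missing rule and the observed-data entry with a Day 1 to Day 28 derivation for ITT patients, applied in this order:

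1. Use the recorded NEWS respiratory rate whenever there is one, including at site visits and on readmission.
2. Count days from death to Day 28 as 0.
3. Count unmeasured days alive and out of hospital after live discharge as below 24, stated as an assumption. The daily hospitalisation status in Protocol 8.1.1 identifies these days.
4. Use LOCF for all other missing days, as in the ICU-stay row, and report by arm the patients excluded because SAP 6.4.2 requires a baseline and a postbaseline measurement.

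Then apply the Wilcoxon test. Add one supportive analysis that varies rule 3, for example carrying forward the last in-hospital rate. Ordinal scale category 2 should not stand in for a high respiratory rate: it records activity limitation or home oxygen.

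The cost is one derivation, its program and one supportive run, on data already collected. The downside is that rule 3 is an assumption and makes the count overlap with duration of hospitalisation.

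If the complete-case analysis is kept, the minimum is to label it complete-case and descriptive, not ITT, and to report the number analysed by arm. That needs only a wording change and a count.
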